#### Non-NIH Collaborators:

[name], Sanofi Genzyme Corporation

[name].	Chief Scientific Officer Executive Vice President, Cellular Therapies [name] [contact] Email: [contact]
[name]	CSO CRISPR Therapeutics CRISPR Therapeutics [name]

[contact]

[name]	Novartis Institute for Biomedical Research [name] [contact] [contact] [contact]	
[name] PhD	Bioverativ [name] [contact] [contact]	
[name].	Editas Medicine [name] [contact] [contact]	
[name].	[name] Lab- [name] [name] [contact]	
Subjects of study:NumberPatients15	SexAge rangeEither18 and above	

#### **Precis:**

The constitution of blood relies upon hematopoietic stem cells (HSCs), which stay in the bone marrow and differentiate to all lineages of peripheral blood cells. HSC transplantation is the only curative option currently available for sickle cell disease (SCD) patients either via allogeneic HSC transplantation or HSC-targeted gene therapy. Granulocyte-colony stimulating factor (G-CSF)mobilized HSCs are frequently utilized in the adult setting of HSC transplantation because of the faster hematologic recovery as compared to bone marrow. As an autologous HSC source for gene therapy, bone marrow harvest has been generally employed since G-CSF has been prohibitive in SCD patients due to granulocyte stimulation and the associated reports of vaso-occlusive crises, multi-organ failure, and death. However, when bone marrow harvest is used, the amounts of collected cells are limited and anesthesia is required. In order to obtain HSCs in large numbers without anesthesia, patients will undergo mobilization followed by large volume apheresis. Plerixafor is an alternative treatment for mobilization without direct stimulation to granulocytes, and it is theoretically applicable for SCD patients. The primary endpoint of this study is to obtain sufficient amounts of HSCs collected from the peripheral blood in SCD patients after plerixafor mobilization with an acceptable safety profile. The harvested products will be stored as backup for patients undergoing gene therapy as well as allogeneic HSC transplantation.

#### 1.0 Introduction and Background

Sickle cell disease (SCD) is the first disease to be described at the molecular level and has long been targeted for treatment at the molecular level. The disease is associated with significant morbidity and early mortality, with the most recent estimates of median lifespan only into the 40s. SCD affects one of every 600 African Americans in the United States alone, with around 100,000 Americans with the disease, but in Africa, an estimated 300,000 births per year are affected by SCD. This orphan disease is historically underserved, and represents an area of significant health disparity.

 $\beta$ -globin is an essential component of hemoglobin, and a specific mutation (20A>T) of  $\beta$ -globin distinguishes SCD. The mutated  $\beta$ -globin leads to hemoglobin polymerization upon deoxygenation in areas of low oxygen tension. As a result, patients develop recurrent pain crisis, anemia, infections, acute chest syndrome, and neurologic events, as well as sudden death as the most serious consequences of this disease. In addition, iron overload due to chronic transfusion increases morbidity and mortality in SCD patients. The medical costs of this disease are enormous, with estimates of \$40,000 per patient per year (year 2000 figures) for chronic red cell transfusion and chelation alone, and rising costs with age at \$231,000 per year in total costs for adults due to accumulating end organ damage have recently been described.

Red cell transfusions are commonly used to treat patients with SCD. Red cells are infused as needed to treat symptoms of anemia, acute and severe complications such as acute chest syndromes and strokes, or before elective surgeries. Red cell transfusions can also be given at timed interval (also known as chronic transfusion therapy) to decrease the incidence of stroke in pediatric patients with abnormal trans-cranial Doppler velocities (internal carotid or middle cerebral artery velocity >200 cm/s). While transfusions can prevent further neurologic events in patients at risk, iron overload is common, resulting in significant end-organ toxicity. Thus, iron chelation has become an important part in the care of patients with SCD.

Hydroxyurea, the one and only FDA approved drug for this disease, results in a significant reduction in the number of pain crisis per year and a decreased frequency of acute chest syndrome, and has become the treatment of choice for many individuals with SCD. Unfortunately, neither red cell transfusions nor hydroxyurea is curative, nor do they appear to reverse established end-organ damage. Hydroxyurea has been suggested to improve survival in patients with SCD. However, life expectancy remains significantly shortened compared to the national average with that of an affected male being 47 years versus the national average of 72.

The only established cure for patients with SCD is allogeneic bone marrow transplantation, and the procedure was initially only applied in children. In adults, the higher burden of accumulated end-organ damage would be expected to result in higher transplantation associated mortality and morbidity. Recently, we established allogeneic hematopoietic stem cell (HSC) transplantation for adult SCD patients, the vast majority of whom meet disease severity entry criteria, by using reduced intensity conditioning. This strategy can cure more than 90% of transplanted SCD patients; however, it requires an HLA-matched sibling donor (without SCD) that can be found for ~10% of patients, leaving 90% of patients with SCD without a curative option.

We are developing both haploidentical allogeneic and autologous HSC-targeted gene therapy for SCD patients who lack an HLA-matched sibling donor. Though we have seen success in around

half of the patients undergoing haploidentical allogeneic transplants, rejection rates remain high, and prolonged cytopenias have been observed in some SCD patients after rejection prompting us to require back up harvests for all patients on this experimental protocol. In addition, we are developing gene therapy approaches which utilize the patients' own HSC. With gene therapy, harvested HSC products are immunomagnetically purified for the CD34+ HSC population, and the purified HSCs are genetically modified to correct the  $\beta$ -globin gene in *ex vivo* culture by gene addition using lentiviral vectors. The genetically modified autologous HSCs are subsequently infused after conditioning. Our initial patients treated with a gene therapy approach have required multiple bone marrow harvests to proceed to transplantation on this protocol which also requires back up bone marrow harvesting.

Peripheral blood is the current preferred source for HSCs in both autologous and allogeneic transplant applications. Mobilization of HSCs into the circulation can be achieved by the administration of granulocyte-colony stimulating factor (G-CSF) and/or plerixafor, allowing the collection of bone marrow derived HSCs from the peripheral blood by apheresis. The mobilized product can be further enriched for the primitive progenitor population by CD34+ cell selection. However, G-CSF leads to intolerable adverse effects in SCD patients including vaso-occlusive crisis, multi-organ failure, and even death, probably due to granulocyte stimulation associated with G-CSF.

Plerixafor is an alternative treatment for HSC mobilization. Plerixafor is an inhibitor of the CXCR4 chemokine receptor and blocks binding of its cognate ligand, stromal cell-derived factor- $1\alpha$  (SDF- $1\alpha$ ). The CXCR4 and SDF- $1\alpha$  play an important role in the homing of human HSCs to the marrow compartment, and the CXCR4 can help to anchor HSCs to the bone marrow matrix. Treatment with plerixafor resulted in elevations in circulating HSCs, and human CD34+ cells mobilized by plerixafor were capable of engraftment with long-term repopulating capacity. Plerixafor can theoretically be applied safely to SCD patients, since it mobilizes HSCs into the peripheral blood without direct stimulation of granulocytes.

Therefore, we sought to evaluate the use of plerixafor to mobilize HSCs in SCD patients. Since our initial publication demonstrating the efficacy of allogeneic transplantation in adults with severe SCD, interest in curative approaches has increased substantially. We have screened more than 750 individuals with SCD at the NIH Clinical Center, and performed transplantation in over 75 SCD patients at our single center. We continue to see 3 new patient screens per week for consideration for protocol entry in our clinical trials testing allogeneic and autologous transplant strategies in this disorder. In this pilot trial, we seek to address one of the major limitations moving forward for autologous gene transfer/editing approaches – autologous HSC harvesting. The ability to safely and reliably collect HSCs in SCD could transform our approach to this devastating disease, meeting a significant unmet need.

# 2.0 Objectives

To obtain sufficient amounts of HSCs collected from the peripheral blood in SCD patients after plerixafor mobilization without serious adverse events.

2.1.Determine the safety profile associated with plerixafor administration in SCD. (Appendix)

- 2.2.Determine the number of CD34+ cells/kg of body weight achievable with plerixafor mobilization in SCD
- 2.3.Compare both the CD34+ cell/kg yield and side effects among SCD individuals

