The risks of plerixafor administration in SCD patients are not known. However, G-CSF administration was reported to induce vaso-occlusive crisis during mobilization in several SCD patients, likely due to granulocyte expansion associated with G-CSF. Tragically, one SCD patient developed multi-organ failure and death after G-CSF mobilization despite close monitoring during the 5 day mobilization. The risks of plerixafor administration, in contrast, are expected to acceptable. Plerixafor has a different mechanism of action and acts by blocking CXCR4 to directly interfere with binding between HSCs and bone marrow niche, while G-CSF markedly increases bone marrow cellularity with granulocyte expansion to permit egress of HSCs to peripheral blood. The different mechanism of plerixafor results in less bone marrow expansion, less granulocyte stimulation, and lower peak of leukocyte counts than G-CSF. Plerixafor effects are brief, with only one time injection at one day, while G-CSF requires injection for 5 days. Bone pain is minimal after a single dose of plerixafor, as compared to very common with 5-6 days of G-CSF.

After single plerixafor administration (240  $\mu$ g/kg) in patients with hematological malignancies, 67% of patients (16/24) achieved sufficient amounts of CD34+ cells ( $\geq$ 2.0x10e6 CD34+ cells/kg) without complication, while a second administration and apheresis was required to obtain a sufficient CD34+ cell yield in 21% of patients (5/24). In addition, a higher dose (480  $\mu$ g/kg) of plerixafor administration in healthy volunteers resulted in greater amounts of HSC mobilization without severe adverse events, as compared to the standard dose (240  $\mu$ g/kg). As compared to these strategies, bone marrow harvest does not require drug administration for mobilization. However, bone marrow harvesting requires anesthesia (similar to surgery), which significantly increases risks of SCD-related complications.

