## 6.0 Treatment Plan

## At NIH

- 6.1 Prophylactic red blood cell exchange or simple red cell transfusions will be given to patients prior to plerixafor administration targeting HbS <30% to reduce the incidence of vaso-occlusive crisis and other events that may be associated with high hemoglobin S levels. Hydroxyurea treatment should be stopped at least 2 weeks before mobilization, since the washout period is important for bone marrow recovery after myelosuppressive effects of hydroxyurea.
- 6.2 Patients undergoing HSC mobilization will be admitted on a telemetry medical unit. They will then receive a single-dose subcutaneous administration of plerixafor (Mozobil®) at 240 μg/kg. (If the CD34+ cell yields are not sufficient for a minimal target dose in each protocol, a second plerixafor administration can be performed at the same dose for mobilization and apheresis the following day.)
- **6.3** Patients will be monitored continuously by telemetry. Leukapheresis will start approximately 4-12 hours after plerixafor is given. Mononuclear cells will be collected using an automated cell separator or apheresis device. Whole blood is withdrawn from one venipuncture site at a rate of 60-80 mL/min and then conveyed to the separator. If IV access is inadequate, central lines will be inserted prior to apheresis. Leukapheresis will be performed by the Apheresis Unit under supervision of the medical staff of the Department of Transfusion Medicine at the NIH Clinical Center with periodic EKG monitoring, or in a nursing unit where continuous cardiac monitoring (telemetry) can start with plerixafor administration and through the apheresis procedure.
- 6.4 After successful blood withdrawal, blood is separated into cells and plasma by centrifugation. The light density mononuclear cells are collected into a component bag, and the remaining cells and plasma are re-infused into the patient via a second venipuncture site. Acid Citrate Dextrose formula A (ACD-A) is used as the anticoagulant at a whole blood to anticoagulant ratio of 13:1. Prophylactic intravenous calcium infusions are used in all procedures. Maximal extracorporeal blood volume during the procedure ranges from

300-400 mL. Sufficient volumes of blood will be processed to obtain target CD34+ cells of 2.0x10e6 CD34+ cells/kg (minimum of 1.5x10e6 cells/kg).

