- **6.5** The harvested peripheral blood apheresis products will be cryopreserved using a controlled rate freezer. All excess cells beyond 2.0x10e6 CD34+ cells/kg will be available for immediate CD34+ cell selection and freezing for research testing cell culture, lentiviral transduction, gene editing, and xenotransplantation.
- 6.6 After successful mobilization and stem cell collection, patients will remain in the hospital for 1-3 days to monitor for side effects. The total inpatient duration is about 1 week. 3-10 days after discharge from hospital, patients will be evaluated in outpatient clinic. Laboratory and other testing will be obtained as clinically indicated.
- 6.7 Additional blood samples may be drawn before plerixafor administration, 2 hours after plerixafor, when starting apheresis, and at the end of apheresis to study CD3, CD34, and total nucleated cell counts. The total amount of blood to be drawn including the screening labs will adhere to the policy for adult patients.
- **6.8** Patients will complete this study 10 days after the last dose of plerixafor, and be taken off this protocol.

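### Does Objective 2.3 go wrong because patients with a low first yield at NIH may be dosed twice?

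*Combined protocol and SAP*

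**What the plan says.** Section 2.0 sets two objectives on yield. Objective 2.2 is to "Determine the number of CD34+ cells/kg of body weight achievable with plerixafor mobilization in SCD", and Objective 2.3 is to "Compare both the CD34+ cell/kg yield and side effects among SCD individuals". The Precis states the endpoint in terms of sufficiency: "The primary endpoint of this study is to obtain sufficient amounts of HSCs collected from the peripheral blood in SCD patients after plerixafor mobilization".

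The two sites collect differently. Section 6.2 (NIH) allows re-dosing: "If the CD34+ cell yields are not sufficient for a minimal target dose in each protocol, a second plerixafor administration can be performed". Section 6.4 sets the aim: "Sufficient volumes of blood will be processed to obtain target CD34+ cells of 2.0x10e6 CD34+ cells/kg", with a minimum of 1.5 in the same units. Appendix II, 6.1 restricts St. Jude to one dose and one apheresis at any yield, and Appendix II, 8.1 allows up to 4 participants there.

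The safety measures follow the whole course. Section 9.0 collects events of grade 3 and above, and SAEs, from the first dose until ten days after the final one. In Section 8.2, pain criterion 1 looks at the length of the whole collection stay, criterion 2 at readmission within ten days of the final dose, and criterion 3 at escalated pain treatment, with no time window.

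Section 8 contains the sample size and the stopping rules. It has no analysis for 2.2 or 2.3.

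**The concern.** At NIH a low first yield can itself cause a second exposure. Yield, number of doses and length of observation are then linked by design, and only at one site. If 2.3 were carried out by setting side effects against yield, poor mobilisers could appear to tolerate plerixafor worse only because they were injected twice. Using first-collection yield would not remove this, because the side effects would still span both doses.

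The yield half is unclear as well. Cumulative yield is the natural measure of sufficiency in the Precis, but it is not the yield of one dose, and a St. Jude patient can have only one.

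Section 3.0 describes the exposure as short: "Plerixafor effects are brief, with only one time injection at one day". A reader of the report may therefore expect a one-dose safety profile. At stake is how a descriptive result is read.

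**Working it through.** **The plan's own figures.** No figure is given for Objective 2.3. The only operating characteristics in Section 8 are Tables 2 and 3. An exact recursion on the cumulative event count over 15 patients reproduces both within 2 points:

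- Table 2, probability of concluding unsafe at true rates 0.50, 0.40, 0.30, 0.20, 0.15, 0.10: 0.963, 0.857, 0.632, 0.331, 0.193, 0.088 (stated 0.96, 0.86, 0.63, 0.33, 0.19, 0.09).
- Table 3, at 0.60, 0.50, 0.40, 0.30, 0.20: 0.972, 0.872, 0.647, 0.342, 0.103 (stated 0.97, 0.87, 0.64, 0.34, 0.10).

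These tables are indexed by the event probability per patient, however many doses that patient has. The concern does not touch them.

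**How many patients might be re-dosed.** Section 3.0 cites a series in hematological malignancy: 16/24 = 67% reached 2.0x10e6/kg after one dose, so 8/24 = 33% did not, and 5/24 = 21% needed a second administration to reach it. Assume these rates carry over to SCD and that the 4 St. Jude places count within the 15:

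- 11 at NIH: 11 × 5/24 = 2.3 to 11 × 8/24 = 3.7.
- All 15 at NIH: 15 × 5/24 = 3.1 to 15 × 8/24 = 5.0.
- Minimum 0, since the second dose is optional and its trigger is a minimal target set in each protocol.

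**How far first-collection and cumulative success could differ.** In the cited series, (16 + 5)/24 − 16/24 = 87.5% − 66.7% = 21 points. With 4 of 15 at St. Jude this becomes 11/15 × 20.8 = 15 points. If every shortfall were re-dosed and converted, the ceilings are 33 points, and 11/15 × 33.3 = 24 points.

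**How unequal the observation is.** The event window is 10 days after one dose and 1 + 10 = 11 days after two on consecutive days. Follow-up after the last dose is 10 days for everyone.

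**Pain criterion 1.** Assume apheresis on the dosing day and the 1 to 3 days of monitoring in Section 6.6. The routine stay is 1 to 3 days after one dose and 2 to 4 after two. One added pain day at the longest routine stay gives 3 + 1 = 4 days (not over 4) or 4 + 1 = 5 days (over 4). So the classification can depend on the number of doses. The example is fragile, though. The excess must be due to pain, Section 6.6 also puts the total stay at about a week, and criterion 3 could classify both patients alike.

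**An illustration that does not size the problem.** Section 10.7.1 gives plerixafor-only rates such as lightheadedness 44%. Two independent doses would give 1 − (1 − 0.44)² = 69%. But these rates cover all grades, while the Section 9.0 window collects grade 3 and above. They also cite the same source (reference 24) as the series in which 5/24 were re-dosed, so they may already mix one-dose and two-dose patients. If the same patients react each time, the increase is 0.

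**What the records allow.** Appendix I has fields for the dates of injections and aphereses. Section 11.7 requires source documents to show dates and details of procedures and adverse events. Re-dosing under 6.2 depends on knowing the first yield, so a first-collection count can be expected to exist, although Appendix I has no field for it.

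**The case for a change.** The strongest case for a change is that the structure is real and nothing in the protocol resolves it. Yield can determine exposure at NIH and cannot at St. Jude, the safety measures span both doses, and Section 8 does not mention it. Re-dosing is foreseeable from the protocol's own citation. Section 10.3 says the study is closed to accrual and in data analysis only, so a descriptive paragraph would be cheap and would alter no dosing, collection or stopping rule.

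The structural facts stand, and so does the ambiguity between first-collection and cumulative yield. The predicted harm does not follow from them. Objective 2.3 names two things to compare among individuals. It does not say that side effects are to be related to yield, or poor mobilisers set against good ones. The safety case also does not depend on a single injection: Sections 1.0 and 3.0 rest it mainly on the absence of direct granulocyte stimulation, and Section 3.0 accepts that risks may add up when mobilisation is repeated.

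The obvious refinement has its own flaw. Splitting a re-dosed patient's events before and after the second dose leaves about one day of first-dose observation, against 10 days for a patient dosed once. Without a common window, that reverses the bias rather than removing it.

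**Conclusion.** This is missing descriptive detail that analysts will fill sensibly, and no change to the plan follows. Unequal exposure is possible by design, for roughly 2 to 5 patients if the cited non-SCD rates apply, and for none if the optional second dose is not used. But the plan specifies no analysis for 2.3 that would return a wrong result, and no test, site comparison or yield-based decision depends on it.

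Precision limits what any formal treatment could add. With 2 events in 5 re-dosed patients, the exact 95% interval is 5% to 85%. At 15 patients or fewer the natural report is a patient-level listing, in which site, number of doses, first and total yield, and events appear together and any link between re-dosing and side effects is plain to see.

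This conclusion assumes that per-collection counts were kept, as 6.2 implies, and that event onset dates are in the source documents, as Section 11.7 requires.

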# 3.0 Scientific and Clinical Justification

Harvest of HSCs is required for both allogeneic HSC transplantation and autologous HSC-targeted gene therapy. Our efforts to develop curative therapies for SCD span this spectrum of modalities, but our efforts are encumbered by the relative contraindication of G-CSF usage in SCD, and thus the most utilized method for HSC collection. The availability of a safe, noninvasive means for HSC harvest from individuals with SCD would accelerate efforts at developing HSC based approaches, and mobilization with plerixafor could fill this void. Thus, the current work seeks to determine the safety of plerixafor mobilization in individuals with SCD undergoing experimental transplantation procedures with haploidentical HSC donors, gene-modified autologous HSCs, or other allogeneic transplant protocol where prolonged cytopenia is expected.

In patients transplanted on our haploidentical transplantation protocol to date, 5 of 21 patients with SCD did not recover their platelet counts to >50k/uL by 100 days' post-transplant. Because of the risk of intracerebral hemorrhage in patients with SCD and severe thrombocytopenia, backup collection of autologous HSCs by bone marrow harvesting is now routinely performed in SCD patients undergoing haploidentical transplantation. Additionally, gene therapy applications targeting autologous HSCs require bone marrow harvesting in SCD subjects, and the experimental nature of this work requires back up harvesting. The need for back up HSCs on these existing protocols demands that patients undergo a bone marrow harvest procedure with the associated risks. This protocol will therefore be offered to patients with SCD enrolling on to our haploidentical transplantation and gene therapy studies as an alternative to bone marrow harvest for collection of autologous HSCs.

The risks of plerixafor administration in SCD patients are not known. However, G-CSF administration was reported to induce vaso-occlusive crisis during mobilization in several SCD patients, likely due to granulocyte expansion associated with G-CSF. Tragically, one SCD patient developed multi-organ failure and death after G-CSF mobilization despite close monitoring during the 5 day mobilization. The risks of plerixafor administration, in contrast, are expected to acceptable. Plerixafor has a different mechanism of action and acts by blocking CXCR4 to directly interfere with binding between HSCs and bone marrow niche, while G-CSF markedly increases bone marrow cellularity with granulocyte expansion to permit egress of HSCs to peripheral blood. The different mechanism of plerixafor results in less bone marrow expansion, less granulocyte stimulation, and lower peak of leukocyte counts than G-CSF. Plerixafor effects are brief, with only one time injection at one day, while G-CSF requires injection for 5 days. Bone pain is minimal after a single dose of plerixafor, as compared to very common with 5-6 days of G-CSF.

After single plerixafor administration (240  $\mu$ g/kg) in patients with hematological malignancies, 67% of patients (16/24) achieved sufficient amounts of CD34+ cells ( $\geq$ 2.0x10e6 CD34+ cells/kg) without complication, while a second administration and apheresis was required to obtain a sufficient CD34+ cell yield in 21% of patients (5/24). In addition, a higher dose (480  $\mu$ g/kg) of plerixafor administration in healthy volunteers resulted in greater amounts of HSC mobilization without severe adverse events, as compared to the standard dose (240  $\mu$ g/kg). As compared to these strategies, bone marrow harvest does not require drug administration for mobilization. However, bone marrow harvesting requires anesthesia (similar to surgery), which significantly increases risks of SCD-related complications.

Following HSC mobilization, apheresis is required for HSC collection. The risks of apheresis are expected to be less than marrow harvest, since apheresis in SCD patients is established for red blood cell exchange. In contrast to simple transfusion, risks of apheresis also include hypovolemia or circulatory overload, citrate toxicity with hypocalcemia, infection, and hematoma or thrombosis at the site of catheter placement. In our current open and active gene therapy protocol, 14-H-0155, the first 4 patients required at least 2 marrow harvests. When repeat HSC mobilization and collection is needed, the risks can be additive, and thus the risk to benefit ratio appears to favor apheresis.

HSC collection by apheresis	HSC collection by bone marrow harvest	
• Central venous catheter placement (all	• General anesthesia, about 2 hours (in all	
patients)	patients)	
• Toxicity from citrate containing	• Inpatient management of postoperative pain	
anticoagulant; hypocalcemia (in 20% of	(in all)	
patients)	• Large intravascular volume shift, about 1-	
• 4-6 hours of apheresis (in all patients)	1.5 liters of marrow are aspirated, replaced	
• Hypovolemia or circulatory volume overload	by equal or greater volume of supportive IV	
(in 20% of patients)	fluid (in all)	
• Hematoma from central venous catheter	• Hematoma (in 20%)	
(<10%)	• Infection (10%)	

Table 1. abbreviated list of adverse events with apheresis or marrow harvest

